Title: Seizure Prophylaxis in Aneurysm Repair (SPAR)

Principal Investigators:

[name], B. [name], [name]

OVERVIEW

Research Objectives:

To examine the utility of levetiracetam (UCB Pharma, Brussels, Belgium) for seizure

prophylaxis in patients undergoing surgical repair of ruptured and unruptured intracranial

aneurysms.

Hypothesis:

No difference exists in seizure frequency post-aneurysm treatment between the levetiracetam and

no levetiracetam groups.

Background information and Rationale:

Seizures are a potential complication of surgical repair of intracranial aneurysms. In order to

prevent seizures, many surgeons administer prophylactic anti-epileptic medications during the

intra-operative and post-operative period; however, such practice is not supported by clinical

data [Raper et al]. A recent retrospective review found that the incidence of postoperative

seizures following intracranial aneurysm surgery was actually higher in those who received anti-

epileptics versus those who did not [Raper et al.]. Given the retrospective nature of this study, it

1

is not certain that both groups were equally at risk for seizures. Older retrospective studies have also suggested that antiepileptic prophylaxis confers no benefit [Sbeih et al., Rhoney et al.]. Recent information on patients undergoing surgery for supratentorial brain tumors has also cast some doubt on the efficacy of seizure prophylaxis. A recent trial randomized 123 patients undergoing craniotomy for resection of supratentorial tumors to either perioperative seizure prophylaxis with phenytoin or no seizure prophylaxis [Lang et al]. These investigators found that prophylactic use of anti-epileptic medication did not reduce the risk of perioperative seizures and was associated with an increased risk of adverse events. They suggested that the routine use of prophylactic anti-epileptic medications in that population may not be indicated.

The strongest argument in favor of routine use of anti-epiletic medications for patients undergoing craniotomy comes from older retrospective reviews that have suggested that rates of post-operative seizures decreased compared with historical controls following the implementation of prophylaxis [Ohman et al., Bidzinski et al.].

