Timeline: Prospective data for subjects will be collected on a secure file with password access for until up to 10 years after all data is published.

Inclusion/Exclusion criteria:

Inclusion:

- 1. Adult (≥18 years)
- 2. Presence of intracranial aneurysm (with or without rupture)
- 3. Patients with unruptured aneurysms must be recommended for microsurgery. Patients with ruptured aneurysms should be recommended for clipping or coiling.

Exclusion:

- 1. History of seizures within last 10 years
- 2. History of epilepsy
- 3. History of prior stroke
- 4. Currently prescribed medication with anti-epileptic activity (keppra, dilantin, tegretol, lamictal, topamax, etc.)
- 5. Brain tumor
- 6. Pregnant or nursing woman
- 7. Known levetiracetam allergy

Recruitment:

All patients seen at the University of Michigan Health System that meet inclusion criteria are currently seen by one of the investigators for routine clinical care. Prior to surgery, the study

will be explained to potential subjects and/or their legally authorized representatives by an investigator or a qualified study team member and they will be able to ask any questions that they may have. In addition, they may contact the PI (by phone, email, or mail). The investigators will recruit from their own patient population. No additional patient recruitment will be pursued.

Design:

Patients that meet all eligibility criteria will be randomized to either a "levetiracetam" or "no levetiracetam" group. There will be no attempt to "blind" the patient or caregivers with respect to group assignment. The group assignment will be known to the patient as well as relevant caregivers.

Patients in both groups will be treated according to all current reasonable clinical practices for the surgical treatment of intracranial aneurysms and its postoperative care. With the single exception of prophylactic levetiracetam administration to only one group, there will be no differences by design between the two groups with respect to treatment.

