Those assigned to the "levetiracetam" group will receive a 500 mg intravenous dose during the operative case and then will be maintained on 500 mg orally twice a day for a total of seven days. Those patients that are assigned to the "no levetiracetam" group will receive no levetiracetam or any other anti-epileptic medications unless the treating physicians determine that such medications are clinically indicated based on specific circumstances. The use of any anti-epileptic medications will be recorded.

As is typical for all patients undergoing craniotomy for aneurysm repair, patients will be monitored in the neurological intensive care unit for at least one day following surgery. The

patients may then be transferred to a ward room where they will continue to be monitored according to standard clinical practices. If a subject is discharged prior to 7 days, periodic chart review and examination at routine clinical follow ups will be used to determine occurrence of seizure. If a seizure occurs in any patient, the seizure will be treated according to best clinical practices as determined by the treatment team without any regard to the patient's group assignment in the study.

A dataset will be prospectively assembled on each patient included in the study. Recorded information will include patient age, gender, location of aneurysm, size of aneurysm, duration of surgery, surgeon's assessment of degree of brain retraction during surgery (on a 3 point scale: less than average, average, more than average), the surgeon's degree of cortical damage during surgery (on a 3 point scale: less than average, average, more than average), the occurrence of an intraoperative hemorrhage, the occurrence of any other unexpected intraoperative events, the dose of levetiracetam and the duration of administration, any side effects or possible side effects of levetiracetam, the dose and duration of administration of any other anti-epileptic medications, the occurrence of any seizures including the number of such events, their duration, their treatment, and their sequelae if any.

Assessments will occur at routine care follow-up visits. These visits typically occur at 1-2 months, 4-6 months, and 6-12 months and up until 5 years +/- 6 months after surgery. Clinical data collected at these visits, specifically, the incidence of seizures, will be used for the study. Additionally, the study team may follow up on any previously reported adverse events.

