Levetiracetam will not be given to half of the study subjects. Although levetiracetam is often used in these patients for seizure prophylaxis, its utility has never been established. A recent randomized trial found that prophylactic administration of antiepileptic medications in those undergoing routine craniotomy for tumor did not reduce the risk of seizures in that population. Therefore levetiracetam administration should not be considered standard treatment and withholding this medication falls within the scope of reasonable clinical practice.

Levitiracetam is associated with side effects in some cases. A recent trial of levitiracetam prophylaxis found that 1 patient had an adverse drug reaction out of 105 patients that were treated with this drug in the perioperative period [Milligan et al].

As with most anti-epileptic medications, levetiracetam appears to have some teratogenic potential. This potential appears to be dose dependent. All women of child-bearing age will undergo pregnancy testing prior to treatment per UMHS routine care practices. Pregnant women will be excluded from this study and will be treated according to standard practices of the treating physician.

There is a risk of loss of confidentiality. This risk is considered minimal and will be reduced by the maintenance of only de-identified data sets on password protected files.

Benefits: Participating subjects may benefit from increased monitoring by the study team as participants in the trial. Subjects in the levetiracetam group may benefit from reduced incidence of seizure. Subjects in the no levetiracetam group may benefit from a reduced indicence of side effects. Additionally, the study will yield important information to the community of physicians and researchers, and ultimately their patients; thus, there will be benefits to society.

ANALYSIS OF DATA

The two groups will be compared to verify that no significant differences in group composition were present. The treatment and no treatment groups will then be compared with respect to the occurrence of seizures including their frequency and duration. The treatment and no treatment groups will be compared with respect to the occurrence of levetiracetam side effects or possible side effects. Significance will be determined at p<0.05.

Up to 100 subjects will be recruited for this study. An interim analysis maybe conducted at any time during this study.

References:

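### No primary endpoint or analysis window is named, so in an unblinded trial the seizure measure and the time horizon can be chosen after results are seen

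*Combined protocol and SAP*

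**What the plan says.** All references are to the combined protocol and SAP.

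- **OVERVIEW, Hypothesis:** "No difference exists in seizure frequency post-aneurysm treatment" between the two groups. There is no time limit, and frequency is not defined.
- **METHODS, Design (treatment):** after an intra-operative dose, patients in the active group are "maintained on 500 mg orally twice a day for a total of seven days". For anyone "discharged prior to 7 days, periodic chart review and examination at routine clinical follow ups will be used to determine occurrence of seizure".
- **METHODS, Design (data recorded):** "the occurrence of any seizures including the number of such events, their duration, their treatment, and their sequelae if any".
- **METHODS, Design (follow-up):** the first routine visit is placed one to two months out and the next at four to six; the later ones run "6-12 months and up until 5 years +/- 6 months after surgery". On how these visits enter the study, the section states: "Clinical data collected at these visits, specifically, the incidence of seizures, will be used for the study".
- **METHODS, Design (end of follow-up):** the final assessment of clinical outcome takes place at routine post-surgical outpatient appointments, with no date or visit fixed. A telephone call seeks clinical status at 5 years; it does not mention seizures by name.
- **METHODS, Design (blinding):** "The group assignment will be known to the patient as well as relevant caregivers".
- **ANALYSIS OF DATA:** "The treatment and no treatment groups will then be compared with respect to the occurrence of seizures including their frequency and duration". Side effects are compared in a separate sentence. One threshold, p<0.05, covers everything. Up to 100 subjects are planned, and an interim analysis is permitted at any time.

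No section labels an outcome primary or secondary, and none names a test, an analysis set or a multiplicity rule.

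**The concern.** A seven-day prophylaxis course raises at least two questions: does it prevent seizures while it is given, and does it change seizure risk over the following years? The same trial can answer these differently, and the plan does not say which one it asks. It also leaves open whether the answer is a proportion of patients, a number of seizures or a duration.

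The team knows the assignments and may look at the data at any time. The reported measure and window could therefore follow the results, either towards an effect or towards the hypothesised absence of one. A reader could not tell a planned result from a selected one.

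Two further problems depend on how the analysis is done:

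- If duration is tested, it exists only for patients who seized, so the test compares subsets selected by outcome and not the randomised groups.
- If follow-up length differs between patients, raw occurrence over all available follow-up estimates risk at no defined time. The Design section makes this likely (visits are described as typical, and the 5-year contact is only attempted) but does not state it.

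**Working it through.** **The plan's own figure.** The only figure is the cap of 100 subjects. It comes with no event rate, effect size or power, so there is nothing to reproduce. The Risks section says half will not receive the drug, which gives 50 per arm. Two-sided testing is assumed.

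**Assumptions.** The documents give no seizure risks for this population, so ranges are used: early risk *e* of 5, 10 or 20% and later risk *l* of 5, 10 or 15%, independent of each other. Cumulative risk is 1 − (1 − e)(1 − l), for example 1 − 0.90 × 0.95 = 14.5%. Seizure counts are geometric (p = 0.6) and durations lognormal (0.5, 0.8). The tests are Fisher's exact for occurrence, tie-corrected Mann-Whitney for counts in all patients, and exact Mann-Whitney for mean duration in patients who seized.

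**No true effect: chance of at least one p<0.05** (range over the nine risk combinations)

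| Tests | Early window only | Early or cumulative |
|---|---|---|
| Occurrence, count and duration | 4.8-9.5% | about 10-15% |
| Occurrence and count | 4.3-5.0% | 7.0-8.6% |
| Occurrence alone, Fisher | 0.7-2.8% | about 2-5% |
| Occurrence alone, uncorrected two-proportion test | about 4-5% | about 7-9% |

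Adding a side-effect comparison at 1/105 per arm (the adverse-reaction rate quoted in the Risks section) does not change the first row. Interim looks are not counted.

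**More windows.** Occurrence alone was tested at 7 days, 2, 6 and 12 months and 5 years, with assumed cumulative risks of 3-10% at 7 days rising to 12-25% at 5 years. The chance of at least one p<0.05 is 12.4-14.0% with the uncorrected test and 3.7-7.1% with Fisher's.

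**True effect: share of trials in which one window gives p<0.05 and the other does not** (occurrence, Fisher)

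| Early risk | Late risk equal in both arms | Late risk also halved |
|---|---|---|
| 10% vs 5% | 7-9% | 9-21% |
| 20% vs 10% | 12-17% | 12-23% |
| 20% vs 5% | 22-35% | 17-27% |

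At 20% vs 5% with late risk 15% in both arms, power is 51% in the early window and 24% in the cumulative one.

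**Duration.** At 10% vs 5%, the expected numbers seizing are 50 × 0.10 = 5 and 50 × 0.05 = 2.5. The smallest two-sided exact rank p-value is 2/C(n1+n2, n1). For 5 vs 2 it is 2/21 = 0.095; for 5 vs 3 it is 2/56 = 0.036. Over the binomial distribution of the two counts, p<0.05 is attainable in only 35% of trials.

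**Precision of an early-window estimate.** Take 5/50 vs 3/50, a difference of 0.04. The Wilson limits are 0.0435 to 0.2136 and 0.0206 to 0.1622. The Newcombe limits are:

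- lower: 0.04 − √[(0.10 − 0.0435)² + (0.1622 − 0.06)²] = −0.077
- upper: 0.04 + √[(0.2136 − 0.10)² + (0.06 − 0.0206)²] = +0.160

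Exact Fisher power at 10% vs 5% is 6.3%.

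**The case against.** The best defence is that the outcome is not really in doubt. There is one hypothesis, and it concerns seizures. The Design section singles out seizure incidence. The analysis section puts seizures first and side effects apart, and its mention of frequency and duration can be read as describing the seizures, not as listing three tests. This stands as far as it goes: the outcome domain is settled. But frequency can mean patients or events, and no horizon is attached to either.

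A second defence is that the window is seven days, or is set by the final assessment. The seven-day sentence says how seizures are found after early discharge; it does not declare a window, and the same section then commits to data up to 5 years. The final-assessment sentence is the nearest the plan comes to an analysis time, but it fixes no date.

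Some stronger readings are tempting and are not supported:

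- **That the plan as written carries a 10-15% error rate.** That range needs duration to be tested, which the text allows but does not clearly require.
- **That three measures at five windows give 1 − 0.95^15 = 54%.** This assumes independent tests, and these are strongly correlated.
- **That testing occurrence alone is safe, or that it is certainly inflated.** Either can be true: it depends on the test, which is not named, and on the number of windows.
- **That discordant verdicts are false positives.** Two prespecified questions with different power will also disagree sometimes. The 35% figure needs a 75% early reduction and no late effect, for which the documents give no support.
- **That outcomes have been or will be selected.** Nothing in the documents shows this.

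**Conclusion.** The point holds. The plan names neither a primary endpoint nor an analysis window, and it applies one p<0.05 to seizure measures collected from a seven-day course out to 5 years, in an unblinded trial.

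On assumed risks, two available windows give a false-positive chance that runs from within the nominal 5% (occurrence alone, Fisher) to about three times it (all three measures tested). The discordance figures show that the choice of window can decide the conclusion when there is a true effect; they do not measure error inflation.

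The text itself establishes the missing endpoint and window. The sizes rest on the assumed risks, counts, durations and tests. This should be corrected, but it is not the trial's decisive weakness: a hypothesis of no difference with at most 100 patients remains hard to support whichever endpoint is named.

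**What to change.** In ANALYSIS OF DATA, name one primary endpoint, one window and one test. For example: the proportion of all randomised patients, by assigned group, with at least one seizure in an early window matched to the seven-day course, reported as a difference with 95% CI. If the longer horizon is the main question, say so and use time to first seizure, censored at last contact.

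Make the other window secondary. Report seizure number and duration descriptively, without p-values, and keep side effects as a separate safety comparison. Check that the data form records seizure date and date of last contact or death. The Design list does not name them, though it need not be complete.

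Do this before outcomes are compared by arm, including at any interim analysis. The investigators are also the treating physicians, so that may no longer be possible. In that case, use a dated amendment that discloses what was already known.

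The cost is a few lines of text and a check of the form. The downside is that an early window has fewer events and a wide interval, such as the −7.7 to +16.0 points shown above. Naming the endpoint makes the result interpretable but adds no power.

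### Seizure duration is compared between arms at p<0.05 but, on the natural reading, only among patients who seized, so it is not a randomised comparison and can mislead in either direction

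*Combined protocol and SAP*

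**What the plan says.** The document is the combined protocol and SAP.

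- **Analysis of Data.** The treatment and no treatment "groups will then be compared with respect to the occurrence of seizures including their frequency and duration". The same paragraph ends: "Significance will be determined at p<0.05". Duration is not marked as descriptive, exploratory or secondary. No analysis set, unit (per seizure, longest, or total per patient) or test is given for it.
- **Methods, Design.** The recorded items include "the occurrence of any seizures including the number of such events, their duration, their treatment, and their sequelae if any". Duration belongs to a seizure event; a patient without a seizure is given no value.
- **Overview, Hypothesis.** It begins "No difference exists in seizure frequency post-aneurysm treatment between the levetiracetam and" and goes on to the untreated group. Duration is not part of it.
- **Size and allocation.** "Up to 100 subjects will be recruited for this study" (Analysis of Data) and "Levetiracetam will not be given to half of the study subjects" (Assessment of Risks and Benefits), so at most about 50 per arm.
- **Blinding.** "The group assignment will be known to the patient as well as relevant caregivers" (Methods, Design). The same section leaves treatment of any seizure to the clinical team.

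**The concern.** Whether a patient seizes is settled after randomisation, and it is the event the drug is given to prevent. The patients who seize on levetiracetam are those whose seizures the drug failed to prevent. The patients who seize without it also include those whose seizures the drug would have prevented. A difference in duration between these two groups can reflect who is left in each group rather than any effect on duration. Recorded duration also depends on how each seizure was managed, and in this trial the managing team knows the assignment.

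At stake is a comparison, and possibly a p-value, printed beside the main seizure result and pointing the wrong way. Naming a primary endpoint would not repair it, because the duration comparison would still stand under the same p<0.05 rule.

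**Working it through.** The plan has no figure of its own to reproduce here. The maximum of 100 comes without a seizure rate, effect size or power, and no calculation for duration is given. All seizure risks and durations below are assumptions. Two-sided testing is also assumed, since the plan does not state sidedness.

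**1. How many patients have a duration.** From the documents: 100 patients, half untreated, so n = 50 per arm. Expected seizers per arm = 50 × risk.

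- 5% risk: 50 × 0.05 = 2.5
- 10% risk: 50 × 0.10 = 5
- 20% risk: 50 × 0.20 = 10

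**2. Smallest attainable p-value.** With a and b seizers in the two arms and no ties, the smallest two-sided exact rank-sum p is 2 / C(a+b, a).

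- 2 vs 5: 2/21 = 0.095
- 3 vs 3: 2/20 = 0.10
- 3 vs 4: 2/35 = 0.057
- 3 vs 5: 2/56 = 0.036
- 4 vs 4: 2/70 = 0.029

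**3. How often p<0.05 is attainable at all.** Let a and b be independent Binomial(50, risk). The first result column sums the probability of all pairs, with a and b at least 1, for which 2 / C(a+b, a) < 0.05. The second is 1 − (1 − (1 − risk₁)^50)(1 − (1 − risk₂)^50).

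| Assumed risk, control vs levetiracetam | p<0.05 attainable | At least one arm has no seizers |
|---|---|---|
| 5% vs 5% | 10% | 15% |
| 10% vs 5% | 35% | 8% |
| 10% vs 10% | 74% | 1% |
| 20% vs 10% | 95% | 0.5% |

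**4. Direction of the bias.** Suppose control risk is 10%, half of control seizures last 30 s and half 120 s, with one seizure per seizer. Mean duration among control seizers is (30 + 120)/2 = 75 s. Total seizure time per randomised control patient is 0.10 × 75 = 7.5 s. Now let the drug halve the risk to 5% in three ways.

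| What the drug prevents | Mean among treated seizers (control 75 s) | Total per randomised treated patient (control 7.5 s) |
|---|---|---|
| All the short seizures | 120 s, up 60% | 0.05 × 120 = 6.0 s |
| Half of each kind | 75 s, no change | 0.05 × 75 = 3.75 s |
| All the long seizures | 30 s, down 60% | 0.05 × 30 = 1.5 s |

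The drug shortens no individual seizure and lengthens none in any row. The seizers-only mean nevertheless shows harm, nothing or benefit, according to which seizures were prevented. Total time per randomised patient is lower on levetiracetam in every row.

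**5. How often the wrong direction would be significant.** The first row of step 4 was simulated with 50 per arm, lognormal durations (log-SD 0.5) and an exact rank test. At 10% vs 5%, about 5% of trials showed significant apparent harm; at 20% vs 10%, about 24%. With all the long seizures prevented instead, significant results favouring the drug on duration occurred at about the same rates (5% and 24%).

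**The case against.** The strongest reply is that the plan never says patients without seizures are left out. It names no analysis set, and total seizure time per randomised patient would fit the same words. That is correct: the seizers-only comparison is an inference. It remains the natural reading, because duration is both recorded and compared as a property of the seizures, and nothing assigns zero to anyone else. If the sponsor intended the total, one sentence would settle it.

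Second, duration is subordinate. It is not in the hypothesis and nothing makes it decide the conclusion. This limits the consequence, but the p<0.05 rule does not exempt it.

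Third, a test that usually cannot reach p<0.05 cannot often declare a false harm. This also stands: about 5% of trials at 10% vs 5%, under a deliberately extreme assumption. A misleading estimate is the likelier outcome than a misleading significant result.

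Two stronger readings should be resisted.

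- A reader might infer that the duration comparison will make a beneficial drug look harmful. The documents say nothing about which seizures levetiracetam prevents, and step 4 shows the bias can go either way or be absent.
- A reader might also infer that seizure number cannot carry a p-value. Counting events as independent would be wrong, since one patient with a cluster could drive the result, but the plan does not say that events are the unit. Number per randomised patient, zeros included, is a valid randomised comparison.

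**Conclusion.** The concern holds for duration. As written, the plan invites a comparison among patients selected by the outcome, under the same threshold as seizure occurrence, and no other section corrects it. That the comparison is not a randomised one rests only on the seizers-only reading, and is true at any seizure rate. The direction of the bias is unknown.

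The sparseness is a separate point and depends on the assumed risk. At 5% to 10% risk and 50 per arm, about 2.5 to 5 patients per arm contribute, and significance is attainable in roughly 10% to 74% of trials. At 20% vs 10% it is attainable in 95%; sparseness then largely disappears, but the selection remains. It would therefore be wrong to say that the duration test can never reach significance. The point merits correction before analysis; it does not by itself undermine the comparison of seizure occurrence.

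**What to change.** Amend the Analysis of Data section as follows.

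1. Make the main test the proportion of all randomised patients, by assigned arm, with at least one seizure.
2. Compare seizure number per randomised patient, with zeros included and the patient, not the event, as the unit. This comparison may keep its p-value.
3. For duration, choose one: report it among patients who seized, descriptively and without a p-value; or replace it with total seizure time per randomised patient, counting zero for those without a seizure.

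Total seizure time mixes how often seizures occur with how long they last, so it should be described as a measure of burden and not of duration alone.

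The Design section already lists the number and duration of seizures among the recorded items, so no new data are needed. The cost is a few sentences and the loss of a p-value on duration among seizers.

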The final assessment of clinical outcome will be made at the time of the regularly scheduled post-surgical outpatient appointments with the surgeon. At that time, the patient data will be de-

identified and entered into the registry. The study team will contact the patient via the telephone to try to obtain their 5-year clinical status.

The patient may be withdrawn from the study at any time if the treating physician or patient does not believe it is in the patient's best interest to continue to participate. All such instances will be recorded.

INFORMED CONSENT

When patients are seen in their physician's clinic for standard clinical care, the study will be explained to them by their physician (a study team investigator) or another qualified study team member and they will be able to ask any questions that they may have. In addition, they may contact the PI (by phone, email, or mail). Patients with ruptured aneurysms will be seen by a study investigator and informed consent may be obtained by an investigator or other qualified study team member.

An attempt will be made by the study team to contact previous participants via telephone to obtain their health status. In this case, a comprehensive telephone consent will be used to collect this information and the interaction will be recorded and maintained in the subject's study record.

PROCEDURES FOR MAINTAINING CONFIDENTIALITY

Data Security: Subjects will be given an ID number after being enrolled in the trial. Their ID number will be used on their data collection sheets. A linkage file will be maintained with patient identifiers to enable the study team to conduct chart reviews to extract data and monitor adverse events. Patient information will be de-identified prior to entry into the database. The database will be password-protected. The linkage file will be maintained in a secure, electronic database

for ten years following the close of the study. At that time, patient identifiers other than study ID will be destroyed.

ASSESSMENT OF RISKS AND BENEFITS

Risks:

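### The only planned safety comparison counts events by their presumed link to levetiracetam and is recorded open label, so it is open to attribution bias against the drug

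*Combined protocol and SAP*

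**What the plan says.** The Design section lists the data to be collected on each patient. Its safety item is "any side effects or possible side effects of levetiracetam". Analysis of Data uses the same drug-related definition: the groups are to be "compared with respect to the occurrence of levetiracetam side effects or possible side effects", with significance at p<0.05 and no test named. The other comparisons planned there are group composition and seizures.

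The trial is open label: "The group assignment will be known to the patient as well as relevant caregivers". Controls are to receive no anti-epileptic medication "unless the treating physicians determine that such medications are clinically indicated based on specific circumstances".

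Adverse events in general are mentioned twice. At follow-up visits, "the study team may follow up on any previously reported adverse events" (Design), and the linkage file is kept "to enable the study team to conduct chart reviews to extract data and monitor adverse events" (Data Security). Neither sentence makes all-cause adverse events a listed data item or a between-group comparison.

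The Benefits paragraph says: "Subjects in the no levetiracetam group may benefit from a reduced indicence of side effects".

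**The concern.** To enter this comparison, an event must first be judged a side effect, or possible side effect, of levetiracetam. That judgement comes naturally for a treated patient. For a control who took none of the drug it is either excluded by definition or left to the recorder. The people reporting and recording know the arm, and the protocol gives no event list, causality criteria, recording window for side effects or blinded adjudication. Two recorders could both follow the protocol and produce different control counts.

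A significant difference could then reflect unequal recording rather than a drug effect. This matters because the trial's hypothesis is that seizure frequency does not differ. If that is the result, the case for withholding levetiracetam rests largely on tolerability, and this is the only planned comparison that addresses it.

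**Working it through.** The plan gives no figure to reproduce: it states no power, event rate, effect size or test. The calculation below is an illustration.

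**Inputs from the protocol**
- Up to 100 subjects, with half not given levetiracetam, so n = 50 per arm.
- Significance at p<0.05.

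**Assumptions**
- Two-sided Fisher's exact test.
- The same true symptom rate q in both arms, so no drug effect.
- A symptom is recorded as a possible levetiracetam side effect with probability a_T in the levetiracetam arm and a_C in control.

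**Formula.** Recorded counts are X_T ~ Binomial(50, q·a_T) and X_C ~ Binomial(50, q·a_C). The chance of a falsely significant result is the sum of P(X_T = i)·P(X_C = j) over all pairs (i, j) with Fisher p<0.05. All 51 × 51 pairs were enumerated.

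For example, with q = 20%, a_T = 80% and a_C = 40%, the recorded rates are 0.20 × 0.80 = 16% and 0.20 × 0.40 = 8%, and the sum is 0.137.

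| True rate q | Recorded, levetiracetam | Recorded, control | Falsely significant |
|---|---|---|---|
| 20% | 100% | 100% | 2.8% |
| 20% | 50% | 25% | 6.3% |
| 20% | 80% | 40% | 13.7% |
| 20% | 80% | 10% | 57.2% |
| 20% | 80% | 0% | 83.2% |
| 20% | 100% | 0% | 95.2% |
| 10% | 100% | 100% | 1.8% |
| 10% | 50% | 25% | 1.2% |
| 10% | 80% | 40% | 4.1% |
| 10% | 80% | 0% | 20.8% |

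**Direction.** With equal recording, false positives split evenly between the arms. With unequal recording, nearly all go against levetiracetam (13.70 of 13.71 percentage points in the 80% against 40% row at q = 20%).

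**Threshold.** If no control event is counted, 6/50 against 0/50 is enough (p = 0.027); 5/50 is not (p = 0.056).

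**Choice of test.** Fisher's test is conservative. With an uncorrected chi-square at q = 20%, the figures are 5.2% for complete recording in both arms, 14.5% for 50% against 25%, and 24.2% for 80% against 40%.

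**Controls who receive levetiracetam.** Start from q = 20% with 80% against 0% recorded, and let exposed controls be recorded like treated patients.
- 10% exposed: 50 × 0.10 × 0.20 × 0.80 = 0.8 control events expected, and 83% falls to 62%.
- 20% exposed: 1.6 events expected, and it falls to 44%.

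**The case against.** The strongest reply is that the symptom rates and recording shares have no source in the documents. The only rate the protocol gives is 1 adverse drug reaction in 105 patients treated perioperatively (Risks). With 1/105 = 0.95% recorded in the levetiracetam arm and none in control, Fisher's test rejects about 0.001% of the time; at 5% against none it rejects 3.8%, still below nominal. This is a fair reason not to attach a particular error rate to the concern. It does not remove it: 1/105 counts reactions attributed to the drug in another study's treated patients, whereas the bias here depends on how common postoperative symptoms are that could be so attributed.

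Second, the dataset covers every patient, and the word possible could admit similar symptoms in controls. On that reading the defect is an undefined term rather than a built-in tilt. The reading is available, and control counts are not fixed at zero, but no rule requires it and the recorders are unblinded. The 83% and 95% figures are therefore upper scenarios.

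Third, side effects are secondary to seizures, the Benefits sentence is not a declared hypothesis, and open-label reporting bias survives any change to the form. All of this stands. It limits the weight of the point: the seizure comparison is unaffected, and the fix reduces the bias without removing it.

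**Conclusion.** The concern holds. The only safety comparison uses an outcome that depends on attribution to levetiracetam, the attribution is made knowing the arm, and no all-cause comparison is planned beside it. The direction of the bias follows from the definition; its size cannot be derived from the documents. On the assumptions above, it is small when recording is mildly unequal or symptoms are uncommon (about 1% to 6% falsely significant) and large when controls are rarely or never counted (57% to 95% at a true rate of 20%). The claim is that the test is open to bias, not that any one of these rates applies. It should be corrected because the correction is cheap and the comparison is the only planned evidence on tolerability.

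**What to change.** Replace the side-effect data item and its comparison with a short list of adverse events fixed in advance, recorded in both arms over the same period regardless of presumed cause. Use the inpatient contacts, chart review and routine visits already planned. Compare the proportion of patients with any listed event, by assigned group, as a risk difference with a 95% confidence interval. Keep the physician's attribution to levetiracetam as a descriptive column. State that a non-significant result will not be read as equal tolerability.

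The cost is a little more data entry, revised wording and more recorded events in the control arm. For patients discharged before day 7, the list relies on the chart and the first routine visit, typically at 1–2 months, so mild events may be missed. Unblinded patients and staff may still report differently.

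Precision also stays poor. With 50 per arm and complete recording, power for an assumed 30% against 20% is about 16% by Fisher's test. A result of 10/50 in each arm gives a Newcombe 95% interval of about −16 to +16 percentage points: each Wilson interval runs from 11.2% to 33.0%, and √(8.8² + 13.0²) ≈ 15.7.
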